### 15.7.4. Treatment duration

Treatment duration is calculated for each patient from the date of randomisation to the date of last day 1 administration + 21 days.

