#### 9.1.1. Overview of the study

The reasons for treatment discontinuation will be reported. Study discontinuation will be described according to the following reasons: adverse event (related or not), death (related or not), progressive disease, lost to follow up, protocol deviation and other reasons.

The patient status (dead, alive, lost to follow-up ) at the cut-off date will be displayed together with each reason of death (progressive disease, adverse event, other).

The number of patients randomised, treated will be presented by treatment group and overall.

Time between randomisation and first administration will be tabulated by treatment arm.

The duration of follow-up is defined as the time elapsed between the date of randomisation and the date of last news or death, death being a censored observation.

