## **9.2. DESCRIPTION DURING THE STUDY**

In arm A, a cycle is defined as 1 administration of vinflunine (day 1) and 14 consecutive days (starting from day 1) of capecitabine doses bi-daily with treatment rescheduled every 3 weeks.

In arm B, a cycle is defined as 14 consecutive days of capecitabine doses bi-daily, with treatment rescheduled every 3 weeks.

Duration of exposure is defined as the time elapsed between the date of 1st intake and the date of last capecitabine (if given) administration + 7 days or day 1 (administration of vinflunine) + 21 days if capecitabine not given.

A summary table will provide by treatment arm, the following items:

- Duration of exposure,
- Number of patient with at least one dose permanently discontinued,
- Number of patient with at least one dose temporarily cancelled,
- Number of patients with at least one dose reduced (including dose delayed and reduced),
- Number of patients with at least one dose delayed (including dose delayed and reduced).

The total number of cycles given during the study, the median number of cycles as well as the number of patients by cycle will be given. The categorized groups of vinflunine and capecitabine doses by cycle will be presented.

The actual dose (mg/m^2) will be calculated from the total dose administered (mg) divided by the BSA. The BSA will be recalculated at each cycle.

The following categories of vinflunine and capecitabine doses will be used:

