**Table 9-2: Categorized bi-daily dose of capecitabine**

Dose category in mg/m 	Dose of capecitabine in mg/m 
Arm A	
> 1250	]1400 – ∞[
1250	]1100–1400]
950	]887.5–1100]
825	] 742.5–887.5]
660	]642.5–742.5]
625	]562.5–642.5]
500	] 437.5–562.5]
<500	] 0–437.5]
Arm B	
> 1250	]1400 – ∞[
1250	] 1100-1400]
950	] 787.5–1100]
625	] 462.5–787.5]
<625	] 0–462.5]

Actual dose intensity (mg/m^2/wk) and relative dose intensity (%) will be calculated per cycle and per patient for the vinflunine plus capecitabine and the capecitabine alone arms. Cumulative dose (mg/m^2) will also be given. Descriptive statistics such as median and range will be provided.

The number and percentage of cycles/patients with a RDI ≤ 90%, in ]90%;100%] or > 100% will also be given.

The actual dose received (mg/m^2) at cycle *i* will be equal to the actual dose received (mg) at cycle *i* divided by the body surface area at the beginning of the cycle *i*.

The body surface area will be calculated as follows:

$$BSA = \frac{(W^{**}0.425 \times H^{**}0.725 \times 71.84)}{10000}$$

where:

- W = Weight (kg) at the beginning of cycle *i*, or last weight available if missing at cycle *i*,
- H = Height (cm) at the beginning of the study.

BSA as per investigator will be used as an estimate when height has not been provided at baseline.

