### 9.2.1. Actual Dose intensity per cycle

Actual dose intensity per cycle will be defined as follows:

$$DI \text{ at cycle } i = \frac{\text{Actual dose received (mg/m}^2\text{) at cycle } i}{\text{Actual duration of cycle } i \text{ (wk)}} = \frac{\text{Actual dose received (mg/m}^2\text{) at cycle } i}{[(\text{Course date at cycle } i + 1) - (\text{Course date at cycle } i)]/7}$$

The duration of the last cycle will be estimated to be 3 weeks.

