### 9.2.3. Actual Dose intensity per patient

Actual dose intensity per patient will be defined as follows :

$$DI = \frac{\text{Cumulative dose (mg/m}^2\text{)}}{\text{Treatment duration (wk)}} = \frac{\sum_{i=1}^n \text{dose}_i}{\sum_{i=1}^n \text{duration}_i}$$

where :

- dosei = actual dose received (mg/m^2) at cycle *i*,
- durationi = actual duration (wks) of cycle *i*,
- n = total number of cycle(s) per patient.

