### **9.2.8. Treatment delay**

The number of patients and cycles delayed will be presented with reason for treatment delay.

A treatment cycle will be considered as delayed if administered  $\geq 4$  days after the planned date with a three weeks interval from day 1 of previous cycle. In arm A, the date of vinflunine administration will determine the day 1 of the cycle; in arm B (and for patients continuing capecitabine alone in arm A), the first day of capecitabine intake will determine the day 1 of the cycle, whatever the first dose has been taken in the morning or the afternoon. Only delay for Day 1 will be calculated.

The delays will be categorized as follows:

- [4 – 7 days[,
- [7 – 14 days[,
- $\geq 14$  days.

The following parameters will be described by arm:

- Number of patients with at least one cycle delayed by four days or more,
- Number of cycles delayed,
- Categorized groups of cycle delay,

- Reasons for cycle delay of four days or more,
- Total number of haematological and non-haematological toxicities, and nature, as per protocol or not, which have led to a dose delay,
- Detail of the haematological and non-haematological toxicities which have led to a delay,

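### SAP 15.7.4 starts treatment duration at randomisation, while SAP 9.2.3 uses the same term for a per-patient dose-intensity denominator that starts at first dose; the plan does not say which applies

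*SAP*

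**What the plan says.** Four parts of the SAP bear on this.

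- **Section 15.7.4 (Appendix 2)** defines the term: "Treatment duration is calculated for each patient from the date of randomisation to the date of last day 1 administration + 21 days".
- **Section 9.2.3** divides cumulative dose by "Treatment duration (wk"), and in the same line rewrites the ratio as summed doses over summed cycle durations. The key reads "duration i = actual duration (wks) of cycle *i".
- **Sections 9.2.1 and 9.2.8** fix what a cycle duration is. A cycle runs from its own course date to the next one, and for the final cycle "The duration of the last cycle will be estimated to be 3 weeks". On the start of a cycle, "In arm A, the date of vinflunine administration will determine the day 1 of the cycle"; in arm B it is the first capecitabine intake.
- **Section 9.2** sorts the results into classes: "The number and percentage of cycles/patients with a RDI ≤ 90"% is one of them, so the class is reported for patients as well as for cycles.

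Two further passages give context. The SAP does not assume that the wait before treatment is zero, since in 9.1.1 "Time between randomisation and first administration will be tabulated by treatment arm". It also has a separate exposure measure that begins with treatment: "Duration of exposure is defined as the time elapsed between the date of 1 st intake".

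**The concern.** One term carries two start dates. The end points match: 15.7.4 stops 21 days after the last day 1, and the summation in 9.2.3 closes with a last cycle of 3 weeks. The definitions therefore differ only by the days between randomisation and first dose, and the equality written in 9.2.3 fails for every patient for whom that gap is not zero.

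A programmer who looks up the denominator named in 9.2.3 finds one definition under that name, in 15.7.4. A programmer who codes the summation gets a different denominator. Both would be following the SAP. Under 15.7.4, days on which no drug was due count as treatment time. That lowers per-patient dose intensity, most strongly in patients with few cycles, and a patient at 100% in every cycle could be shown well below 100% in the per-patient table. After amendment PA06 the remaining analysis is descriptive PFS and safety, and the dose-intensity tables help a reader to interpret the toxicity.

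**Working it through.** **Inputs from the SAP.** Planned doses per cycle are in Tables 9-3 and 9-4: vinflunine 280 mg/m²; capecitabine 825 × 2 × 14 = 23100 mg/m² (arm A) and 1250 × 2 × 14 = 35000 mg/m² (arm B). The theoretical cycle is 3 weeks. The RDI classes are in 9.2.

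**Assumed input.** The wait g from randomisation to first dose. The documents available give neither a length nor a limit, so 0 to 14 days is used as a range.

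**Step 1: the plan's own figures.** Planned dose intensity is planned dose divided by 3: 280/3 = 93.33; 23100/3 = 7700; 35000/3 = 11666.67 mg/m²/wk. All three match Tables 9-3 and 9-4.

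**Step 2: the 9.2.3 summation.** Take a patient with full doses exactly every 21 days for n cycles, and read the course date of 9.2.1 as the day 1 of 9.2.8. The denominator is 21n days, so RDI = 21n/21n = 100% for every n and every g.

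**Step 3: the 15.7.4 definition.** For the same patient the last day 1 falls g + 21(n − 1) days after randomisation. Adding 21 gives a denominator of 21n + g days, so RDI = 21n/(21n + g).

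| Wait g (assumed) | n=1 | n=2 | n=3 | n=4 | n=6 | n=10 |
|---|---|---|---|---|---|---|
| 0 days | 100% | 100% | 100% | 100% | 100% | 100% |
| 3 days | 87.5% | 93.3% | 95.5% | 96.6% | 97.7% | 98.6% |
| 7 days | 75.0% | 85.7% | 90.0% | 92.3% | 94.7% | 96.8% |
| 14 days | 60.0% | 75.0% | 81.8% | 85.7% | 90.0% | 93.8% |

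**Step 4: when the class changes.** RDI is 90% or less when 21n ≤ 0.9(21n + g), that is, g ≥ 21n/9 = 2.33n days. In whole days the threshold is 3, 5, 7, 10, 12 and 14 for n = 1 to 6, and 24 for n = 10.

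**Step 5: the same effect in mg/m²/wk.** For n = 6 and g = 7 the denominator is 19 weeks instead of 18. Vinflunine falls from 93.33 to 1680/19 = 88.42, capecitabine in arm A from 7700 to 138600/19 = 7295, and capecitabine in arm B from 11667 to 210000/19 = 11053.

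**The case against.** The best defence is that 9.2.3 already settles the matter. It is the section devoted to this measure, it defines every symbol in its formula, and it does not refer to 15.7.4. Section 9.2.4 builds the planned intensity cycle by cycle, which fits the summation. Section 15.7.4 is a single line in an appendix, placed under toxicity, and does not mention dose intensity. A programmer who codes the explicit formula gets 100% for the patient above. This stands, and it makes the effect conditional. It does not remove the conflict: 9.2.3 still names a denominator that the SAP defines differently elsewhere, and in the text available 9.2.3 is the only place where that term enters a calculation.

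A reader might infer three stronger things that the documents do not support.

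- *That waiting days do lower dose intensity under this plan.* This would require 15.7.4 to override the summation, and nothing says that it does.
- *That the extra day in 15.1 lowers RDI further.* Section 15.1 does list treatment duration, but its formulas are for months and years. The dose-intensity denominator is in weeks, and 9.2.1 gives its own date difference without an added day.
- *That the arms would be distorted unequally because an infusion starts later than a tablet.* No passage gives the wait in either arm; 9.1.1 only promises to tabulate it.

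**Conclusion.** The contradiction is real and its consequence is conditional. If 15.7.4 is used, per-patient RDI for a full-dose, on-schedule patient is 21n/(21n + g), and the patient is put in the class of 90% or less once the wait reaches 2.33 days per cycle given. If the 9.2.3 summation is used, nothing changes. The size depends on a wait that the documents do not state.

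The reach is narrow: the by-patient dose-intensity table in Appendix 1 and any listing that carries the per-patient values. Per-cycle DI and RDI, cumulative dose, duration of exposure, PFS and adverse event incidences do not use this denominator. Since the whole analysis is now descriptive and exploratory, the point is minor, but it should be settled before the table is programmed.

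**What to change.** In SAP 15.7.4, replace randomisation as the start date by the date of first study drug administration (cycle 1 day 1). Add that, for dose intensity, treatment duration equals the sum of the cycle durations in 9.2.1, with the last cycle counted as 21 days. Sections 9.2.3 and 15.7.4 then give the same denominator, and the 9.2.3 formula needs no change.

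The cost is one or two sentences of SAP text and a check that the per-patient program uses the summation. No new data are needed, because the first administration date is already required for the table in 9.1.1.

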## 15.8. END OF STUDY

### 15.8.1. Death for progression

In case of death for progression (so PD documented in the tumour assessment form and death documented in death report form are at the same date), the reason for treatment discontinuation is **Progression**.
